In blood and/or saliva, biomarkers related to the HPA axis activation including but not limited to adrenocorticotrophic hormone (ACTH) and cortisol, neurotropic factors, inflammation and metabolic factors may be investigated.

Biomarker essays may be added or deleted based on scientific information or technical innovations under the condition that the total volume of blood collected will not be increased.

The biomarker evaluations will include blood collection for genetic/pharmacogenomic and epigenetic testing to characterize gene expression in relation MDD symptoms and biomarker results. Participation in the genetic/pharmacogenomic part of this study is mandatory.

SAFETY EVALUATIONS

The collection of AEs and concomitant medications will start after the ICF has been signed and will continue until the final visit. AEs of special interest include pruritus and gastrointestinal (GI) complaints such as dyspepsia, abdominal pain, constipation, or diarrhea. If these are of moderate or severe intensity (sufficient discomfort to cause interference with normal activity and/or warrant treatment), investigators should provide a narrative to describe the event. At a minimum, a description of the event (including any known precipitating circumstances), the time relative to dose administration, the duration, concomitant treatment, and outcome of the event will be reported.

Apart from this, the following safety assessments will be done: physical examination, neurological examination, body weight, vital signs (including temperature), 12-lead electrocardiogram (ECG), urine drug testing, pregnancy testing (female subjects only), clinical labs (hematology, chemistry panel, gastric mucosa integrity panel) and urinalysis. At screening only: serology, thyroid function, and HbA1c (diabetic subjects only).

Additional blood and urine samples may be taken or vital signs and ECGs recorded at the discretion of the investigators.

Additionally, emergence of suicidal ideation will be assessed using the Colombia suicide severity rating scale (C-SSRS) at screening, and during each study visit. Arizona Sexual Experiences (ASEX) will be used to document sexual dysfunction and the Karolinska Sleepiness Scale (KSS) will be used to document sleepiness/sedation.

STATISTICAL METHODS

Sample size determination

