The CPFQ (Fava 2009) is a brief self-report scale that provides additional information regarding the impact of adjunctive treatment on aspects of cognitive and executive function including attention, memory and mental acuity. Subjects with MDD are often reported to have difficulties with functioning in this area.

DNA Collection

It is recognized that genetic variation can be an important contributory factor to interindividual differences in drug distribution and response and can also serve as a marker for disease susceptibility and prognosis. Pharmacogenomic research may help to explain interindividual variability in clinical outcomes and may help to identify population subgroups that respond differently to a drug. The goal of the pharmacogenomic component is to collect deoxyribonucleic acid (DNA) to allow the identification of genetic and/or epigenetic factors that may influence PK, PD, safety and/or tolerability of JNJ-67953964, and to identify genetic and epigenetic factors associated with neuropsychiatric/neurodegenerative disorders. Genes and epigenetic

changes in genes known to be in pathways relevant to depression (HPA axis, inflammation, growth factors, monoamine transporters, ion channels, circadian rhythm) also will be evaluated.

DNA samples may be used to help address emerging issues and to enable the development of safer, more effective and ultimately individualized therapies in the future. Pharmacogenomic data obtained from this study may also be included in an ongoing cross-study analysis to investigate the relationship between depression severity and phenotypes and biomarkers.

Safety assessments

Standard safety assessments including physical and neurological examination, vital signs, 12-lead ECG, clinical chemistry, hematology, and urinalysis will be performed. Based on observations of gastrointestinal (GI) complaints in previous studies, a panel including pepsinogen I (PGI), pepsinogen II (PGII), gastrin-17 (G17) and helicobacter IgG antibodies (Hp IgG) will be added to the clinical laboratory test panel to test for stomach mucosa status (Agréus 2012, Syrjänen 2017).

Additionally, emergence of suicidal ideation will be assessed using the C-SSRS (Posner 2007). The C-SSRS has been used frequently in clinical studies and is a standard measure for suicidal ideation assessment according to FDA guidance (US FDA 2012).

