6. Subject has received an investigational drug (including investigational vaccines) or used an invasive investigational medical device within 3 months before the planned first dose of

^a This section has been amended by amendment INT-1, INT-2 and INT-3

study drug, or has participated in any interventional clinical studies on MDD in the previous 1 year, or is currently enrolled in an interventional study.

7. Has signs or symptoms of Cushing's Disease, Addison's Disease, primary amenorrhea, or other evidence of significant medical disorders of the HPA axis.
8. Is breast feeding.
9. Subject has a history of malignancy within 5 years before screening (exceptions are squamous and basal cell carcinomas of the skin and carcinoma in situ of the cervix, or malignancy that in the opinion of the investigator, with concurrence with the sponsor's study responsible physician, is considered cured with minimal risk of recurrence).
10. Has one or more of the following diagnoses:

- A primary DSM (5th edition) diagnosis of:
 - GAD
 - panic disorder
 - obsessive compulsive disorder (OCD)
 - posttraumatic stress disorder (PTSD)
- Subjects with comorbid GAD, SAD, or panic disorder for whom MDD is considered the primary diagnosis are not excluded.
- A current diagnosis or diagnosis in the past 1 year of:
 - psychotic disorder
 - MDD with psychosis
 - anorexia nervosa or bulimia nervosa.
 - chronic fatigue syndrome
 - bipolar disorder (BD)
 - mental retardation
 - antisocial or borderline personality disorder
 - autism spectrum disorder.

11. Has a current or recent history of clinically significant suicidal ideation within the past 6 months, corresponding to a score of 4 (active suicidal ideation with some intent to act, without specific plan) or 5 (active suicidal ideation with specific plan and intent) for ideation on the C-SSRS, or a history of suicidal behavior within the past 1 year, as validated by the C-SSRS at screening or Visit 2. Subjects with a prior suicide attempt of any sort, or prior serious suicidal ideation/plan > 6 months ago, should be carefully screened for current suicidal ideation and only included at the discretion of the investigator.

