7.3. Participant Discontinuation/Withdrawal from the Study^a

A participant will be withdrawn from the study for any of the following reasons:

- The investigator or sponsor believes (e.g. that for safety or tolerability reasons such as a SAE at least possibly related to the study drug) it is in the best interest of the subject to discontinue the study.
- Increased or intolerable symptoms of depression
 - At the discretion of the investigator after the subject reported a “much worse” or “very much worse” condition using the self-assessment of treatment experience or
 - $\geq 30\%$ increase of MADRS score (compared to Visit 2) during the double-blind treatment period.
- The subject becomes pregnant.
- A subject will be discontinued from the study if the QTcF interval is higher than 500 msec or is prolonged >60 msec from the baseline value. QTc interval prolongation should be confirmed by collecting 2 additional ECGs as soon as possible after the initial ECG. The average value of the QTcF interval of the three ECG's will be used to determine whether a subject should be discontinued. If the QTcF is not readily available, the QTcB may be used instead. The subject will continue to be monitored (maximum 12 hours) by repeated 12 lead ECGs (at least every 60 minutes) until the ECG normalizes.
- A subject who shows signals of clinically meaningful acute suicidal ideation at any time during the study should be withdrawn from the study and referred for appropriate medical/psychiatric care.
- A subject will be discontinued from the study if the liver function tests exceed the values as presented in Section 10.7.

Also, a participant will be automatically withdrawn from the study for any of the following reasons:

- Lost to follow-up
- Withdrawal of consent. When a subject withdraws consent, effort should be made to determine if the cause of withdrawal was due to tolerability or lack of efficacy.
- Noncompliance to take the study medication. Noncompliance will be decided on a case-by-case basis depending on the number of missed capsules and the interval between missed doses.

Subjects who drop out, other than for safety reasons related to the study drug or study procedures, will be replaced if the number of subjects completing the study will be below 96. A maximum of 32 subjects (1/3 of targeted subjects) will be allowed to be replaced. Replacement

^a This section has been amended by amendment INT-3

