9.5. Safety Analyses

Statistical analysis of the safety data will be done by the sponsor or under the authority of the sponsor. Specific details will be provided in the Statistical Analysis Plan.

All safety analyses will be performed based on the safety analysis set, which will include all randomized subjects who receive at least 1 dose of study drug. Safety summaries will be provided by treatment, unless specified otherwise.

AEs will be coded using the current version of Medical Dictionary for Regulatory Activities (MedDRA) and tabulated by system organ class, by severity and relationship to study drug and will be presented by treatment. SAEs will be summarized separately.

The safety analysis will include the incidence of AEs, actual data and changes in blood pressure, pulse rate, laboratory safety data, 12-lead ECG and physical and neurological examination data from predose to all postdose assessments.

The suicidal ideation and suicidal behavior data collected from the C-SSRS will be summarized descriptively at each scheduled timepoint by treatment group. Sexual dysfunction (ASEX) and KSS data collected will be summarized descriptively at each scheduled timepoint by treatment group.

Adverse Events

The verbatim terms used in the CRF by investigators to identify AEs will be coded using the MedDRA. All reported AEs with onset during the double-blind treatment phase (i.e., TEAEs, and AEs that have worsened since baseline) will be included in the analysis. For each AE, the percentage of subjects who experience at least one occurrence of the given event will be summarized by treatment group. Summaries will be provided for all subjects receiving at least one dose of study drug in this study, and will include AEs from this study.

Summaries, listings, datasets, or subject narratives may be provided, as appropriate, for those subjects who die, who withdraw due to an AE, or who experience a severe AE or a SAE.

Clinical Laboratory Tests

Laboratory data will be summarized by type of laboratory test. Descriptive statistics will be calculated for each laboratory analyte at baseline and at each scheduled time point, and for changes from baseline.

The number and percentage of subjects experiencing a laboratory result below or above normal reference ranges will be provided for each laboratory analyte by treatment group. Summaries will be provided for all subjects receiving at least one dose of study drug in this study.

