A listing of subjects with any laboratory result outside the reference ranges will be provided.

ECG

Heart rate and ECG intervals (RR, PR, QRS and QT) as well as corrected QT intervals according to Bazett's formula (QTcB) and Fridericia's formula (QTcF) (Bazett 1920, Sagie 1992, Hodges 1983, International Conference on Harmonization [ICH] 2005) from the 12-lead ECG will be summarized at baseline and at each scheduled time point and for changes from baseline using descriptive statistics.

The number and percentage of subjects with at least one occurrence of a treatment-emergent potentially clinically important QTc measurement (QTc value >450 , >480 , or >500 msec) or with a change from baseline in QTc >30 msec or 60 msec, will be summarized by treatment group.

Data listings of subjects with any potentially clinically important values or with a change from baseline in QTc will be provided.

Vital Signs

Descriptive statistics of temperature, pulse, and blood pressure (systolic and diastolic) values and changes from baseline will be summarized at each scheduled time point. The percentage of subjects with values beyond clinically important limits will be summarized.

Physical and Neurological Examinations

Subjects with abnormal findings will be presented in a data listing.

Other Safety Measures

C-SSRS

The suicidal ideation and behavior data collected from the C-SSRS will be summarized descriptively at each scheduled timepoint by treatment group. Data from the subjects with suicidal ideation and behavior will be presented in data listing.

ASEX and KSS

Sexual dysfunction and KSS data collected will be summarized descriptively at each scheduled timepoint by treatment group.

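### The C-SSRS is meant to assess emergence of suicidal ideation, but the supplied documents plan only by-visit summaries and a listing, with no count per arm of subjects new or worse on randomised treatment

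*Protocol*

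**What the plan says.** **Purpose.** The synopsis states that "emergence of suicidal ideation will be assessed using the Colombia suicide severity rating scale (C-SSRS) at screening, and during each study visit". Protocol section 4.2 repeats the aim: "Additionally, emergence of suicidal ideation will be assessed using the C-SSRS".

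**Analysis.** C-SSRS analysis is described in three places: the synopsis, the opening text of section 9.5, and the C-SSRS paragraph under Other Safety Measures in 9.5. All three give the same descriptive summary by visit and arm. The last reads "The suicidal ideation and behavior data collected from the C-SSRS will be summarized descriptively at each scheduled timepoint by treatment group". The synopsis and that paragraph add a listing: "Data from the subjects with suicidal ideation and behavior will be presented in data listing". None mentions change or shift from baseline, a worst post-baseline category, a treatment-emergent definition or an any-time incidence.

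**Entry and withdrawal.** Exclusion criterion 11 (section 5.3) covers recent ideation "corresponding to a score of 4 (active suicidal ideation with some intent to act, without specific plan) or 5", and suicidal behaviour in the past year. Section 7.3 states: "A subject who shows signals of clinically meaningful acute suicidal ideation at any time during the study should be withdrawn from the study". The Time and Events Schedule places the C-SSRS at screening, at every visit, and in a single column shared by Visit 11 and early withdrawal.

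**Deferral.** Section 9.5 leaves the specifics of safety analysis to the SAP. The SAP supplied is a population PK and exposure-response plan. Its safety scope is pruritus, gastrointestinal complaints and possibly other adverse events of grade 3 or higher, and it does not mention the C-SSRS.

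**The concern.** Emergence is a within-subject idea: something new or worse than before treatment. A table of who reports ideation at each visit is a prevalence table. It can be read for emergence only if nobody starts with ideation and nobody leaves because of it. Neither condition holds here, since lower-level ideation is compatible with entry and acute ideation leads to withdrawal.

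The plan treats other safety measures in the same section differently. Adverse events are counted as subjects with at least one occurrence. QTc is counted as subjects with at least one treatment-emergent value. Laboratory values and vital signs are given as changes from baseline. The C-SSRS, which section 2.3 names among the measures against suicidality risk and section 8.4.5 describes as important monitoring, has none of these.

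At stake is a number that a reader of the study report would expect: how many subjects in each arm had new or worse ideation or behaviour during the six randomised weeks.

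**Working it through.** **1. What a by-visit table cannot separate.**
- Criterion 11 excludes ideation scores 4 and 5, so scores 1 to 3 may enter. At a later visit, a subject unchanged from entry and a subject newly affected fall in the same cell.
- A subject withdrawn under section 7.3 counts where the ideation is recorded, then leaves the numerators and denominators of later visits.
- An early-withdrawal rating shares the Visit 11 column. Visit 11 is Day 78, which SAP section 4.6 places in the withdrawal period, when all subjects take placebo. No rule says whether an early-withdrawal rating made during randomised treatment is tabulated there, at the nearest visit, or not at all.
- No C-SSRS baseline is named. Visit 2 and the treatment baseline differ, because every subject first passes through a placebo lead-in.

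**2. The plan's own sample size, used only to size the arms.**
- Protocol 9.1: effect size 0.45, power 90%, one-sided alpha 0.20. n per arm = 2 × (0.842 + 1.282)² / 0.45² = 44.5, rounded up to 45. This reproduces the stated 45 (90 in total).
- 90 / 0.95 = 94.7, rounded up to 95, or 96 when made even for 1:1 allocation. This matches the stated 96.
- 96 / (0.75 × 0.90) = 142.2, matching the stated 142.
- Lead-in responders are randomised too, so all randomised = 142 × 0.90 = 127.8, or about 64 per arm. (SAP Table 1 plans 71 of 142 with PK data, making no allowance for lead-in dropout.)

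**3. Illustration A: possible dilution.** The rates are assumptions: emergence in 10% on drug and 4% on placebo, spread evenly over the five post-baseline treatment visits (Days 29, 43, 50, 57 and 64, from the SAP).
- Cumulative: 0.10 × 64 = 6.4 and 0.04 × 64 = 2.6 subjects.
- Every emergent case withdrawn at detection: 6.4 / 5 = 1.3 and 2.6 / 5 = 0.5 subjects at each visit.
- No case withdrawn and all persisting: the visit count builds from 1.3 versus 0.5 at the first visit to 6.4 versus 2.6 at the fifth. Nothing is lost by the end, but these subjects are still mixed with those who had ideation at entry.

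**4. Illustration B: with ideation at entry.** This is a simulation of 64 per arm and five visits, again on assumed rates. Ideation is present at treatment baseline in 10%, 20% or 40% and is reported again at each visit with probability 0.6. New onset among the remaining subjects is 5% on placebo and 15% on drug. Each new case is withdrawn after the visit where it appears.

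| Ideation at baseline | Placebo, by visit | Drug, by visit | Difference at a visit |
|---|---|---|---|
| 10% | 6.9–7.2% | 8.8–9.8% | 1.9–2.6 points |
| 20% | 12.8–13.3% | 14.4–15.9% | 1.6–2.7 points |
| 40% | 24.7–25.3% | 25.8–28.0% | 1.0–2.7 points |

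A subject-level count of new cases shows about 5% versus 15%. A 10-point difference therefore appears as about 1 to 3 points at any one visit.

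**The case against.** Five objections narrow the point.

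1. **The deferral.** Section 9.5 says it is not the full specification. Other items left to the SAP, such as the ANCOVA sensitivity analyses and the anhedonia cutoffs, are also absent from the PK plan supplied, so a separate clinical SAP may exist. This stands: a reader might infer that the trial will never report treatment-emergent ideation by arm, and the documents do not support that. They show only that no supplied text plans it.

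2. **Adverse event reporting.** Section 8.4 requires clinically relevant changes to be recorded as adverse events, and 9.5 counts these per subject by arm. Ideation serious enough for withdrawal should be captured. A reader might infer that such cases are counted nowhere, and that would be wrong. But this route depends on investigator reporting and would miss lower-grade shifts. It also covers onset over the whole 11-week double-blind phase, including the placebo lead-in and withdrawal periods.

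3. **Early withdrawal.** A C-SSRS is scheduled at that visit, so withdrawn subjects are not without a final rating. What remains open is where the rating is tabulated.

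4. **Visible starting levels.** Visit tables include screening and Day 1, so pre-treatment prevalence can be seen by arm, and the listing keeps each case traceable. Neither gives a planned incidence of new or worse ideation by arm.

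5. **Constructed size.** Only clinically meaningful acute ideation triggers withdrawal, so emergent scores of 1 to 3 may stay and recur. The fivefold dilution is a worst case and should not be read as expected. Nor would the proposed count be a powerful test: 6/64 versus 3/64 gives a two-sided Fisher p of 0.49. Its value is descriptive.

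**Conclusion.** The point holds in limited form. The stated purpose is emergence. The only C-SSRS analyses in the supplied documents are by-visit summaries by arm and a listing, and these do not yield the number of subjects per arm who are new or worse during randomised treatment. That rests on the text and on no assumed rate.

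The size is not known. On the assumed 10% versus 4%, a single visit shows between 1.3 versus 0.5 subjects (all withdrawn at detection) and, at the last visit, 6.4 versus 2.6 (none withdrawn, all persisting), before subjects with ideation at entry are added.

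It would go too far to conclude that an imbalance in serious suicidality would be missed. Serious cases should reach the adverse event tables, every case is listed, and individual monitoring and withdrawal do not depend on these tables. This is a cheap improvement to the analysis plan. It does not affect the primary result.

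**What to change.** The change is statistical only; entry and withdrawal rules stay as they are. In section 9.5 and the synopsis (or by confirming that a clinical SAP already does this):

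- Add, by arm on the safety analysis set, the number and percentage of subjects whose worst C-SSRS category in the six-week randomised period is new or worse than their worst category over a stated reference period before the first randomised dose. Show ideation and behaviour separately, as shift tables.
- State that reference period. The screening form in Appendix 11a has lifetime and past-6-month columns, and the lead-in adds further ratings. A lifetime reference would class recurring ideation as not new.
- Assign early-withdrawal and unscheduled ratings to a period by date, not by the Visit 11 column.
- Show the placebo withdrawal period separately.
- Keep the by-visit tables and the listing as support.

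The cost is a few extra tables and some wording. The C-SSRS is already collected at screening and at every visit, so no new data are needed.

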9.6. Interim Analysis

An interim analysis may be executed. The procedures for the interim analysis will be described in a separate charter.

A blinded data review for purpose of sample size re-estimation may be performed during the study after minimally 50% of the subjects are randomized and have completed Week 6 of the double-blind treatment period. Sample size may be re-adjusted if the observed SD substantially deviates from the hypothesized SD or if the lead-in response and dropout rate substantially deviate from the assumed values. The maximal number of subjects to be enrolled in the trial will not surpass 180.

10. SUPPORTING DOCUMENTATION AND OPERATIONAL CONSIDERATIONS

10.1. Appendix 1: Abbreviations

ABV	Alcohol-by-volume
ACTH	Adrenocorticotropic hormone
AE	Adverse Event
ALKS	Alkermes
ALT	alanine aminotransferase
AMA	Anti-mitochondrial antibody
ANA	Antinuclear antibody
ANCOVA	Analysis of covariance
ANOVA	Analysis of variation
Anti-HAV (IgM)	Anti-hepatitis A virus (Immunoglobulin M)
Anti-HEV (IgM)	Anti-hepatitis E virus (Immunoglobulin M)
AP	Alkaline phosphatase
ASEX	Arizona sexual experiences scale
ASMA	Anti-smooth muscle antibody
AST	Aspartate transaminase
ATRQ	Antidepressant Treatment History Questionnaire
AUC	Area under the plasma concentration-time curve (time period specified by subscript).
BBB	bundle branch block
BD	Bipolar disorder
BDNF	Brain-derived neurotropic factor
BMI	Body mass index
BUN	Blood urea nitrogen
CBC	Complete blood count
CERC	Cerecor
CGI-S	Clinical Global Impression – Severity
CHF	Congestive heart failure
CI	Confidence interval
Cmax	maximum drug concentration
CMV	Cytomegalovirus
CNS	Central nervous system
CPFQ	Cognitive and Physical Functioning Questionnaire
CPK	Creatine phosphokinase
CRP	C-reactive-protein
C-SSRS	Columbia Suicide Severity Rating Scale
CV	coefficient of variation
CYP	cytochrome P450
DILI	Drug induced liver injury
DM	Diabetes mellitus
DNA	desoxyribonucleic acid

DRC	Data Review Committee
DSM-IV/5	Diagnostic and Statistical Manual of Mental Disorders fourth/fifth edition
EBV	Epstein-Barr virus
ECG	Electrocardiogram
(e)CRF	(electronic) case report form
eDC	Electronic data capture
EF	embryo/fetal
eITT	Enriched intent-to-treat (population)
EOT	End-of-treatment
ERCP	endoscopic retrograde cholangiopancreatography
ESR	Erythrocyte sedimentation rate
FDA	Food and Drug Administration
fITT	Full intent-to-treat (population)
FSH	follicle stimulating hormone
FT4	Free thyroxine
G17	gastrin-17
GAD	General anxiety disorder
GCP	Good Clinical Practice
GGT	Gamma-glutamyltransferase
HAM-A	Hamilton Anxiety Scale
HAM-A6	6 item subscale from HAM-A
HBsAg	Hepatitis B surface antigen
HCV	Hepatitis C antibodies
HDRS17	Hamilton rating scale for Depression-17
HIV	Human immunodeficiency virus
HPA	Hypothalamus pituitary adrenal
Hp IgG	helicobacter IgG antibodies
hs-CRP	High-sensitivity C-reactive protein
IB	Investigator's Brochure
ICD	International Classification of Diseases
ICF	Informed consent form
ICH	International Conference on Harmonization
IEC	Independent Ethics Committee
IRB	Institutional Review Board
IGF1	Insulin-like growth factor 1
IL-X	Interleukin-X (1 β , 2, 6, 10...)
INR	International normalized ratio
IUD	Intrauterine device
IUS	Intrauterine system
IWRS	Interactive web response system
KOR	kappa opioid receptor
KSS	Karolinska Sleepiness Scale
LC-MS/MS	Liquid chromatography/mass spectrometry/mass spectrometry

LDH	Lactic acid dehydrogenase
LFT	liver function test
LKM	Liver kidney microsomal antibody
LKM1	Liver kidney microsomal antibody type 1
LOQ	Limit of quantification
LT	Liver test
MADRS	Montgomery Asberg Depression Rating Scale
MAOI	Monoamine oxidase inhibitor
MDD	Major Depressive Disorder
MDE	Maximum desired mean exposure
MedDRA	Medical Dictionary for Regulatory Activities
MINI	Mini International Neuropsychiatric Interview
MMRM	Mixed-effects model for repeated measures
MOS	Margin of Safety
MRCP	magnetic resonance cholangiopancreatography
MRI	Magnetic resonance imaging
MTD	Maximum tolerated Dose
NOAEL	no-observed-adverse-effect-level
NSAID	Nonsteroidal anti-inflammatory drug
OCD	Obsessive compulsive disorder
OTC	Over the counter
pANCA	Anti-neutrophil cytoplasmic antibody
PD	pharmacodynamics(s)
PET	Positron emission tomography
PGI/II	pepsinogen I / II
PK	Pharmacokinetic(s)
popPK	Population Pharmacokinetics
PPI	Proton pump inhibitor
PQC	Product Quality Complaint
PRN	As needed
PRO	Patient reported outcome
PT	Prothrombin time
PTSD	Post-traumatic stress disorder
PTT	Partial thromboplastin time
QD	Once daily
RBC	Red blood cell
RNA	ribonucleic acid
SAD	Social anxiety disorder
SAE	Serious adverse event
SAMe	S-adenosyl methionine
SATE	Self-Assessment of Treatment Experience
SD	Standard deviation
SHAPS	Snaith-Hamilton Pleasure Scale

SIGH-A	Structured Interview Guide for the Hamilton Anxiety scale
SIGMA	The Structured Interview Guide for the MADRS
SMDDS	Symptoms of Major Depressive Disorder Scale
SNRI	serotonin-norepinephrine reuptake inhibitor
SRP	Study responsible physician
SSRI	Selective serotonin reuptake inhibitor
SUSAR	suspected unexpected serious adverse reaction
Tbili	Total bilirubin
TEAE	Treatment-emergent adverse event
TES	Time and Events schedule
TIBC	Total iron binding capacity
TNF α	Tumor necrosis factor alpha
TSH	thyroid-stimulating hormone
ULN	Upper Limit of Normal
US	United States
VAS	Visual Analogue Scale
WBC	White blood cell
WOCBP	women of childbearing potential

